#### 3.4.5.1 Part 1 Treatment Emergent Adverse Events

The Medical Dictionary for Regulatory Activities (MedDRA) dictionary will be used to classify all adverse events reported during the study by system organ class (SOC) and preferred term

(PT). Analysis of treatment-emergent adverse events from Part 1 (Part 1 TEAE) will include all new or worsening adverse events with date of onset during or after the date of first study drug administration through the end of Part 1. Part 1 TEAE summaries will exclude adverse events with date of onset after the Week 16 visit date or date of onset more than 30 days after the date of last study drug administration for patients who discontinue treatment. Part 2 TEAE summaries will exclude adverse events with date of onset more than 30 days after the date of last study drug administration for patients who discontinue treatment. Adverse events will be summarized by SOC and PT. Tables and listings will summarize adverse events occurring in Part 1 and 2 separately. Drug-related AEs, SAEs, and serious drug-related AEs will be summarized accordingly. Multiple occurrences of the same event will be counted once for each patient at the level of SOC and the level of PT.

Adverse events by SOC, PT, and severity will also be summarized. Multiple occurrences of the same event will be counted once for each patient by preferred term under the highest severity.

In the presence of partial dates, the available data (month and/or year) will be compared to the appropriate study reference dates to identify the most likely study period.

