11.6. Recording Adverse Events

All conditions present prior to the administration of the first dose of study drug (Day 1) should be documented as medical history. After the first dose, documentation of adverse events (AEs) shall continue until 30 days following administration of the final dose of study medication, regardless of the relationship of the AE to study drug. Information to be collected includes type of event, date of onset, date of resolution, Investigator-specified assessment of severity and relationship to study drug, seriousness, as well as any action taken.

While an AE is ongoing, changes in the severity (e.g., worsening and improving) should be noted in the source documents, but when documenting the AE, only the total duration and greatest severity should be recorded in the eCRF. AEs characterized as intermittent require documentation of onset and duration.

All drug-related (Possible or Probable, see Section 11.4) AEs and abnormal laboratory test results reported or observed during the study must be followed to resolution (either return to baseline or within normal limits). All other AEs will be followed through the final visit indicated in Table 3 or Table 4 and Table 5 or Table 6, as appropriate.

AEs resulting from concurrent illnesses, reactions to concurrent illnesses, reactions to concurrent medications, or progression of disease states must also be reported. Preexisting conditions (present before the start of the AE collection period) are considered concurrent medical conditions and should NOT be recorded as AEs. However, if the patient experiences a worsening or complication of such a concurrent condition, the worsening or complication should be recorded as an AE. Investigators should ensure that the AE term recorded captures the change in the condition (e.g., “worsening of...”). Any improvement in condition should be documented as per Section 9.10.12.

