### 3.3 Analysis of Treatment Group Comparability

Demographic information (age, sex, ethnicity, race), baseline characteristics (baseline BMI, weight) and baseline disease characteristics (including PAH classification and details, time since diagnosis, baseline PAH concomitant medications, thromboembolic disease assessment, pulmonary function testing, oxygen use during 6MWTs and available baseline right heart catheterization data) will be summarized by treatment arm for all randomized patients.

Descriptive baseline summaries of continuous data will present the group mean, standard deviation, median, minima, and maxima. Descriptive summaries of discrete data will present the category counts as frequencies and percentages.

Unless otherwise stated, the baseline value of any variable will be defined as the last available value recorded prior to the first administration of bardoxolone methyl/placebo. Missing values will not be imputed, unless otherwise noted, and will be tabulated as missing.

### 3.4 Analysis of Part 1

Part 1 data will be analyzed using the analysis populations defined in [Section 3.1](#). Separate analyses will be performed by each cohort. Part 1 analyses will only include data from the placebo controlled portion of the study. If a subject does not complete Part 1, or chooses not to enter Part 2, then all their data will be used in Part 1. If a subject enters Part 2, then all data up to and including the Week 16 visit will be included in Part 1.

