### 3.4.3 Concomitant Medications

The WHO Drug Dictionary will be used to classify all medications recorded during this study. Medications taken from 28 days prior to the administration of the first dose of bardoxolone methyl/placebo through the final follow-up visit will be recorded in the concomitant medication forms. The numbers and percentages of patients who had taken any baseline concomitant medications (i.e., start date on or before study Day 1 and stop date after Day 1) will be summarized by medication for each treatment arm. The numbers and percentages of patients who had started taking any post-baseline concomitant medications during Part 1 (i.e., start date after study Day 1 through Week 16) will be summarized by medication for each treatment arm. Study medications with start date after Week 16 will be excluded from the Part 1 summaries of concomitant medications, unless the patient did not continue into Part 2.

In the presence of partial dates, the available data (month and/or year) will be compared to the appropriate study reference dates to identify the most likely study period.

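### SAP 3.4.5.1 contradicts SAP 3.4 and 3.4.3 on whether post-Week 16 adverse events count in Part 1 for completers who do not enter Part 2

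*SAP*

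**What the plan says.** Three SAP rules decide which post-Week 16 data belong to Part 1.

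- **SAP 3.4.5.1 (treatment-emergent adverse events).** "Part 1 TEAE summaries will exclude adverse events with date of onset after the Week 16 visit date". The same sentence also excludes events with "date of onset more than 30 days after the date of last study drug administration for patients who discontinue treatment". It states no exception for completers who stop at Week 16.
- **SAP 3.4 (Analysis of Part 1).** If a subject does not complete Part 1 "or chooses not to enter Part 2, then all their data will be used in Part 1". The Week 16 limit is tied to the other group: "If a subject enters Part 2, then all data up to and including the Week 16 visit will be included in Part 1".
- **SAP 3.4.3 (concomitant medications).** Medications started after Week 16 "will be excluded from the Part 1 summaries of concomitant medications, unless the patient did not continue into Part 2".

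On the collection side, Protocol 11.6 says that adverse event documentation "shall continue until 30 days following administration of the final dose of study medication". Protocol 7.1 schedules a follow-up visit four weeks after the last dose for patients who do not go on to Part 2. It lists those who completed Part 1 and declined the extension separately from those who stopped drug during Part 1.

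**The concern.** The rule that builds the adverse event tables is the only one of the three without the exception for patients who do not continue. Two programmers working from the same SAP could therefore produce different Part 1 adverse event and serious adverse event tables. One would follow 3.4.5.1 and stop at the Week 16 visit. The other would follow 3.4 and count through follow-up. A literal reader would also tabulate a drug started during follow-up to treat an event, but not the event itself.

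Safety and tolerability against placebo is a secondary objective. Whether a serious event in the month after the last dose enters the incidence table should not depend on which section the programmer happens to apply.

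**Working it through.** The plan gives no figure to reproduce. The check sets the rules side by side and then does simple arithmetic on the length of the collection window.

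**Step 1. Where a post-Week 16 event is counted, by type of patient**

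| Patient | SAP 3.4.5.1, literal | SAP 3.4 |
|---|---|---|
| Stops drug before Week 16 | Part 1, to 30 days after last dose | Part 1, all data |
| Completes and enters Part 2 | Not Part 1 (Part 2 instead) | Not Part 1 (Part 2 instead) |
| Completes and chooses not to enter Part 2 | Not Part 1 | Part 1, all data |
| Completes but is ineligible for Part 2 | Not Part 1 | Not named |

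The rules conflict in the third row. In the fourth row 3.4.5.1 excludes the events and 3.4 is silent.

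**Step 2. Could the Part 2 tables pick these events up?** SAP 3.5.5 defines Part 2 events as new or worsened after the Week 16 visit and reports them under BARD and PBO-BARD. SAP 3.5 rests those groups on every Part 2 patient receiving active drug, and Appendix B limits Part 2 output to Part 2 data with no cumulative summaries. A completer who goes home has no Part 2 data. Counting by date alone would put a placebo patient who never took active drug into PBO-BARD, which cannot be intended. So the Part 2 tables do not recover the events.

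**Step 3. Is a completer a discontinuer?** SAP 3.4.2 defines completing Part 1 as completing the Week 16 visit while on treatment, with the last dose allowed up to two weeks before that visit. Together with the two groups in Protocol 7.1, this points to treating completers and discontinuers as different patients.

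**Step 4. Length of the disputed period for one such patient**

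Inputs: Week 16 is Day 112 (protocol schedule of assessments); the follow-up visit is 28 days after last dose (Protocol 7.1); documentation runs 30 days after last dose (Protocol 11.6). Assumption: last dose near Day 112.

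Share = days after Week 16 ÷ total collection days.

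- To the follow-up visit: 28 / (112 + 28) = 28/140 = 20%.
- To the end of documentation: 30 / (112 + 30) = 30/142 = 21%.
- If the last dose was two weeks before the visit, at Day 98, documentation ends at Day 98 + 30 = 128. The disputed part is 128 − 112 = 16 days, and 16/128 = 12.5%.
- Under SAP 3.4, for a patient who chooses not to enter Part 2: 0 days.

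These are shares of one patient's calendar days, not of events. Neither the number of such patients nor their events is given, so the effect on any incidence or between-arm difference cannot be computed.

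**The case against.** A reader might infer that these events are certain to appear in no table and that harm is therefore understated. The documents do not support either claim.

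- **SAP 3.4 already addresses most of the group.** It covers Part 1 analyses generally and assigns to Part 1 all data of those who choose not to continue. Loss follows only if 3.4.5.1 overrides 3.4, and the SAP does not say that it does. This stands, and it makes the finding a contradiction rather than a settled loss.
- **The 30-day clause can be read more widely.** It refers to patients who discontinue treatment without adding that they stop early, whereas SAP 3.4.2, 3.4.4 and 3.4.5 say so when they mean it. A completer who declines Part 2 also stops drug. This reading is possible, but Step 3 counts against it, so the ambiguity remains.
- **The ineligible group is narrow.** The missed-dose limits in Protocol 9.4 match the interruption limits in Protocol 9.9, beyond which a patient interrupted for toxicity should be discontinued from the study and so gets the tail. What is left is the Week 16 completer who fails the compliance rule for other reasons. This stands as a limit on size.
- **Bias is not shown.** Nothing indicates that completers who go home tolerated treatment worse. The rule applies to both arms, and the disputed time is largely off drug. This stands.
- **A Week 16 boundary has a rationale**, because the objective concerns 16 weeks of treatment. That is only a partial answer: discontinuers get a 30-day tail, which for a late stopper runs past Day 112.
- **The events are not hidden.** SAP 2.3 puts all collected data in by-patient listings, serious events are reported within 24 hours, and the safety review committee sees all available data. This stands, but listings do not give incidence by arm.

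**Conclusion.** Wrong as written: a safety derivation rule contradicts the general Part 1 data rule and its concomitant-medication counterpart, and the SAP gives no order of precedence. Read literally, 3.4.5.1 leaves about 28 to 30 days of collected follow-up, 20% to 21% of the window, out of every adverse event summary for each completer who does not enter Part 2. That assumes a last dose near Day 112; the share falls to 12.5% if dosing ended two weeks earlier. Under SAP 3.4 nothing is lost for those who choose not to continue, while completers ineligible for Part 2 are left without a stated exception. The effect on the comparison with placebo is unknown, because the documents give neither the number of such patients nor their events. The point concerns an ambiguous derivation, not demonstrated bias.

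**What to change.** In SAP 3.4.5.1, state that the Week 16 cut applies only to patients who enter Part 2. For every patient who does not enter Part 2, for any reason, Part 1 treatment-emergent events include onset up to 30 days after last dose. Reword the condition in SAP 3.4 in the same way, from choosing not to enter Part 2 to not entering it, so that ineligible completers are covered there too.

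This aligns 3.4.5.1 with 3.4, 3.4.3 and the collection period in Protocol 11.6. The cost is a sentence or two in the SAP and one derivation flag. No new data are needed.

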Several lines of evidence suggest that Nrf2 activation can increase mitochondrial respiration and biogenesis, in addition to inducing expression of numerous antioxidative genes to counter reactive oxygen species (ROS). Specifically, by increasing the availability and production of reducing equivalents such as NADH and FADH₂, Nrf2 activation improves mitochondrial ATP production and improves the efficiency of mitochondrial respiration and oxygen consumption. In addition, Nrf2 activation results in improved beta-oxidation of fatty acids and improved uptake of glucose, which leads to improvement in mitochondrial respiration, oxygen consumption, and energy production. Furthermore, Nrf2-mediated induction of PGC1 α , a master transcriptional coactivator and central inducer of mitochondrial biogenesis, by bardoxolone methyl is hypothesized to increase mitochondrial biogenesis and energy production.

Approved PH therapies act to promote vasodilation of pulmonary arteries and through reductions in pulmonary resistance and right-sided cardiac pressure, these therapies have indirect effects on vascular and cardiac remodeling. Given the degree of parenchymal and vascular fibrosis and remodeling in interstitial lung disease (ILD) patients, vasodilation therapies are minimally effective in treating pulmonary hypertension in those patients. Notably, none of the approved therapies target the metabolic and mitochondrial dysfunction. [REDACTED]

[REDACTED] Approved PAH therapies tested have no significant effects on the tested parameters of mitochondrial function. Thus, bardoxolone methyl may provide a novel approach to PH therapy through improvements in bioenergetics and mitochondrial function that translate to increased muscular function and exercise capacity in PH patients, including those with interstitial lung disease.

From a safety perspective, apart from fluid retention observed in advanced CKD patients with specific risk factors, bardoxolone methyl appears to possess a favorable clinical safety profile compared to existing PAH therapies. Bardoxolone methyl does not have primary systemic hemodynamic depressor effects and is therefore unlikely to promote systemic hypotension or syncope. The available preclinical and clinical data also indicate that bardoxolone methyl does not cause liver toxicity. A nonhuman primate developmental toxicity study of bardoxolone methyl demonstrated no adverse effects on embryo-fetal development.

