5.1.2. Fluid Overload

Similar to ERAs in certain patient populations, including bosentan in advanced congestive heart failure and avosentan in advanced CKD, bardoxolone methyl treatment was found to be associated with an increased risk for fluid overload and heart failure hospitalizations in the BEACON trial, which enrolled patients with Stage 4 CKD (eGFR 15-29 mL/min/1.73 m²) and type 2 diabetes. The overall increased risk for fluid overload and heart failure events with bardoxolone methyl appeared to be limited to the first three to four weeks after initiation of treatment. Elevated BNP and prior hospitalization for heart failure were identified as risk factors that contributed to increased risk for these events. The increased risk for these events from bardoxolone methyl treatment had not been observed in six previous CKD studies, which were mostly conducted in patients with Stage 3b CKD (eGFR 30-44 mL/min/1.73 m²), patients with hepatic dysfunction, cancer patients, or healthy volunteers.

Review of admission notes and narrative descriptions for heart failure hospitalizations in BEACON indicates that heart failure in bardoxolone methyl-treated patients was often preceded by rapid fluid weight gain (several kilograms within the first weeks of treatment initiation) and was not associated with acute renal decompensation or acutely reduced left ventricular contractility. Available data from BEACON and other studies suggest that bardoxolone methyl treatment can differentially affect hemodynamic status according to the clinical condition of patients and likely promotes fluid retention in patients with more advanced renal dysfunction and other recognized risk factors associated with heart failure at baseline. This current study will employ risk mitigation procedures to reduce the potential for bardoxolone methyl-induced fluid overload, including exclusion of patients with the identified risk factors and close monitoring for fluid retention within the first month of treatment.

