9.3.2. Permitted Medications

Allowed concomitant medications include the following:

- Antibiotics;
- Daily multivitamins or recommended daily supplements;
- Other medications intended to manage concurrent diseases, as authorized by the treating physician;
- Medications intended to manage interstitial lung disease or sarcoidosis in patients enrolled in Cohort 4 (PH-ILD cohort), including but not limited to methotrexate, prednisone, nintedanib, or pirfenidone;
- Medications approved for treatment of WHO Group I PAH intended to manage pulmonary hypertension in WHO Group III and WHO Group V patients;
- Oral, implantable, or injectable contraceptives.

Patients taking medication chronically should be maintained on those same doses and dose schedules throughout the study period, as medically feasible.

The use of the following therapies, which may affect PH, are permitted during the study, provided the patients have been receiving a stable dosage for at least 30 days prior to Day 1. Unless medically indicated, the doses of these agents should remain unchanged during the study.

- Vasodilators (including calcium channel blockers);
- Digoxin;
- L-Arginine supplementation;
- Diuretics;
- Agents to treat anemia (including but not limited to supplemental iron, erythropoietin, or intravenous iron);
- If the patient receives intravenous iron therapy during Screening, the intravenous infusion must be performed at least 30 days prior to Day 1;

- Agents to treat neuropathic pain associated with peripheral neuropathy (such as pregabalin);
- Oxygen supplementation.

Corticosteroids are allowed if the patient has been receiving a stable dose of ≤ 20 mg/day of prednisone (or equivalent dose, if other corticosteroid) for at least 30 days prior to study Day 1. If receiving treatment for CTD with any other drugs, doses should remain stable for the duration of the study.

PAH-specific background therapy should be taken as clinically indicated and prescribed by the physician for the duration of the study.

Diuretics may be prescribed as clinically indicated throughout the study. Any changes to the doses of diuretics throughout the course of the study must be recorded in the eCRF.

Patients who fulfill the requirements, as defined above, should not be withdrawn from the study solely on this basis. Consultation with the medical monitor should occur prior to withdrawing a patient from the study.

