9.6.3. Protocol Safety Review Committee

A Protocol Safety Review Committee (PSRC) will assess the starting dose and each new dose level of bardoxolone methyl for safety and tolerability based on review of all available data for this study at the time of each review. PSRC reviews will occur after the Week 4 data are available for the first eight patients enrolled at each new dose level combined across Cohorts 1 and 2 (i.e., the 6MWD \leq 450 m and 6MWD $>$ 450 m cohorts). Upon completion of the dose ranging portion of the study, the PSRC will continue to meet at regular intervals (approximately quarterly) to monitor safety of all patients, including those enrolled in Cohorts 3 and 4.

The PSRC will include at a minimum a Sponsor representative, a cardiologist, and a statistician. Should issues arise requiring expertise not represented by the current members, the PSRC may appoint additional clinical specialists.

The PSRC will assess the following to escalate:

- Signs and symptoms of fluid overload, including adverse events (edema, dyspnea, etc.), weights, and BNP;
- All other collected safety laboratory test data and vital sign measurements;
- Pharmacodynamic markers of Nrf2 activation, including transaminase, GGT, and ferritin levels.

Doses or exposures associated with the defined dose levels in this protocol have been studied previously in healthy volunteers, oncology patients, patients with hepatic dysfunction, and patients with moderate CKD without untoward toxicity. Therefore, the PSRC will assess for general safety and specific signs and symptoms of fluid overload. The PSRC assessment will include a dose level recommendation based on clinical evaluation of the above specified assessments for subsequent cohorts to escalate to a higher dose, proceed to a lower dose, or maintain the current dose. The PSRC may also recommend stopping dosing for current cohorts.

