Each AE should be recorded to represent a single diagnosis. Accompanying signs (including abnormal laboratory test values or ECG findings) or symptoms should NOT be recorded as additional AEs. If a diagnosis is unknown, sign(s) or symptom(s) should be recorded as an AE(s). Changes in laboratory test values or ECG parameters are only considered to be AEs if they are judged to be clinically significant (i.e., if some action or intervention is required or if the Investigator judges the change to be beyond the range of normal physiological fluctuation). If abnormal laboratory test values or ECG findings are the result of pathology for which there is an overall diagnosis (e.g., increased creatinine levels in renal failure), only the diagnosis should be reported as an AE.

Elective procedures (surgeries or therapies) that were scheduled prior to the start of AE collection are not considered AEs. These elective procedures should not be recorded as AEs, but should be documented in the patient's source documents as elective (e.g., elective periodontal surgery). However, if a pre-planned procedure is performed early (e.g., as an emergency) because of a worsening of the preexisting condition, the worsening of the condition should be captured as an AE.

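### The readable SAP safety text gives fluid overload, the drug's main identified risk, no pre-specified per-patient count by arm, and diuretic dose increases no stated summary by arm

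*SAP*

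**What the plan says.** **Protocol.** Section 5.1.2 reports that "bardoxolone methyl treatment was found to be associated with an increased risk for fluid overload and heart failure hospitalizations in the BEACON trial". Section 5 describes the safety profile as favorable "apart from fluid retention observed in advanced CKD patients with specific risk factors". Section 9.1.1 sets up home weights, a 2.3 kg stop-and-assess trigger and a review of the diuretic regimen at early signs of volume overload. Section 9.3.2 adds: "Any changes to the doses of diuretics throughout the course of the study must be recorded in the eCRF". For escalation decisions, section 9.6.3 has the Protocol Safety Review Committee (PSRC) look at "Signs and symptoms of fluid overload, including adverse events (edema, dyspnea, etc.), weights, and BNP".

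**SAP.** Section 3.4.5.1 states "Adverse events will be summarized by SOC and PT", with further splits by severity, drug relationship and seriousness. Its counting rule is "Multiple occurrences of the same event will be counted once for each patient at the level of SOC and the level of PT". Section 3.4.3 builds the Part 1 medication table from "patients who had started taking any post-baseline concomitant medications during Part 1 (i.e., start date after study Day 1 through Week 16"), listed by medication. Section 3.5.3 is likewise based on medications started. Section 3.4.5.5 summarizes weight by visit with descriptive statistics. Sections 3.4.5.1 to 3.4.5.7 run without a numbering gap. None of them contains a grouped term list, a count of patients with fluid overload or a diuretic summary.

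**The concern.** The protocol treats fluid overload as one condition seen through several signs: edema, weight gain, dyspnea, BNP and heart failure. The SAP reports adverse events term by term. A patient with edema, one with recorded weight gain and one with cardiac failure may fall in different rows under different system organ classes, and no row says how many patients had any of these. A diuretic dose increase is a further trace of the same condition. It is collected but has no stated place in the by-arm tables when the diuretic was already in use at baseline.

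The primary objective depends on this. SAP 1.5.2 chooses the dose range by clinical judgment, seeking the best efficacy among doses whose safety is acceptable. That judgment is better served when the main known risk is counted once per patient and by arm. A term list assembled after the data have been seen would also be open to a charge of selection. Some sponsor personnel are unblinded (protocol 9.6), and analyses may be run as data accumulate (SAP 1.9).

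**Working it through.** **1. The plan's own figures.** 8 × 3/4 = 6 active patients per dose group, and 1/6 = 16.7%, printed as 16%. 38 + 16 + 6 × 24 = 198. These agree with the protocol. Neither document gives an expected fluid-overload rate, a safety alpha or a safety power.

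**2. Which planned table would give the count?**
- Adverse events: a patient is counted once per preferred term and once per system organ class. Terms sharing a class are combined; terms in different classes are not.
- Recording rule (protocol 11.6): one diagnosis per event. Separate signs or symptoms are recorded only when no diagnosis is known, so the same condition can enter under different terms.
- Medications: a newly started diuretic is counted. A raised dose of a baseline diuretic is not, unless the site enters it as a new record with a new start date; even then the direction of the change is not shown.
- Weight: by-visit statistics do not count patients above the protocol's 2.3 kg threshold. Suppose 30% gain 2.3 kg by Week 4 and the rest lose 1 kg (protocol 5.1.5 reports about 1 kg per month in CKD with diabetes). The mean change is 0.30 × 2.3 − 0.70 × 1 = −0.01 kg. The quartiles and maximum would show spread, but not the number of patients.

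**3. Sizes of the SAP's pooled groups (SAP 1.8).**
- All PAH, planned: Cohorts 1 and 2 have 54 patients at 3:1, giving 40.5 v 13.5. Cohorts 3a and 3b have 48 at 2:1, giving 32 v 16. Total 72.5 v 29.5, taken as 72 v 30.
- All PH, planned: 4 × 24 = 96 at 2:1, giving 64 v 32.
- All PAH, maximum: 40.5 + 96 = 136.5 v 13.5 + 48 = 61.5, taken as 136 v 62.

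**4. Illustration of dilution.** The probability of separation is the sum of Bin(i; nA, pA) × Bin(j; nP, pP) over all outcomes with i/nA > j/nP and a two-sided Fisher p ≤ 0.05. The rates, the 0.05 criterion and the even split, with each patient in exactly one row, are assumptions.

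| Group | Combined, 24% v 6% | Each of 2 rows, 12% v 3% | Each of 3 rows, 8% v 2% | Each of 4 rows, 6% v 1.5% |
|---|---|---|---|---|
| All PAH, 72 v 30 | 0.52 | 0.15 | 0.03 | 0.01 |
| All PH, 64 v 32 | 0.58 | 0.21 | 0.07 | 0.02 |

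**5. Sensitivity.**
- At 30% v 10% in All PAH, the planned size gives 0.55 combined, 0.07 for each of three rows and under 0.01 for each of five. The maximum size gives 0.90, 0.30 and 0.10.
- With the same 18-point excess over a 20% or 30% background, the combined row falls to 0.38 or 0.36 in All PAH and to 0.39 or 0.35 in All PH.
- In a single subcohort of 16 v 8, the combined row at 24% v 6% gives about 0.01.

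**The case against.** A reader might infer that patients managed by raising an existing diuretic drop out of the safety report. The documents do not support that. Protocol 11.6 requires worsening of a pre-existing condition to be recorded as an adverse event, and SAP 3.4.5.1 includes new or worsening events. The edema or volume overload that prompts a diuretic change is itself reportable. What lacks a by-arm count is the dose change.

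A reader might also infer that fluid overload is never tabulated or examined as a whole. That is too strong. Class totals combine terms within a class, and SAP 2.3 puts all eCRF data in by-patient listings. The PSRC reviews fluid-overload events, weights and BNP together, unblinded. Protocol 11.7 provides aggregate review of common events, including edema and fluid retention. The mock tables and the PSRC plan were not available, and redacted exploratory or efficacy text could cover natriuretic peptides or clinical worsening. Nor do the documents say that diuretic changes are recorded in order to measure fluid overload. That is an inference from protocol 9.1.1 and 9.3.2.

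The size also has limits. The even, exclusive split is a worst case. If one patient's signs are recorded separately, that patient appears in several rows and the row rates rise. Protocol 11.7 lists dyspnea and edema as common in this population, so a broad composite carries background. A figure of 80% power can be obtained at 24% v 6% by pooling Cohorts 3 and 4 (96 v 48), but the SAP defines no such group.

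All of this stands. What remains is that the PSRC review serves escalation and ongoing safety monitoring, and the aggregate review serves expedited reporting. Neither is a defined by-arm outcome in the final report.

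**Conclusion.** The concern holds in a limited form. On the readable text, the SAP has no pre-specified by-arm count of patients with fluid overload and no stated by-arm summary of dose increases of a baseline diuretic. The information is collected and can be recovered from tables and listings, but a reader of the final report would have to assemble it.

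The figures above show dilution under assumed rates; they are not the power of a planned analysis, because safety is descriptive and no adverse-event test is specified. They also assume that the related terms are coded to different system organ classes. At the planned sizes and 24% v 6%, the combined row is informative but far from decisive, and it is weaker still if background rates are high. This is a cheap improvement to an exploratory Phase 2 plan, not an error that invalidates its safety analysis. If the mock tables already contain a grouped fluid-overload table, that part of the point falls away.

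**What to change.** - **SAP 3.4.5.1:** add one by-arm table of patients with any event from a MedDRA fluid-overload term list, fixed before unblinding for the clinical study report. Present it for the SAP's own groups (All PAH, CTD-PAH, non-CTD PAH, All PH). Show each component and the union, with nonspecific terms such as dyspnea on separate lines.
- **SAP 3.4.3:** add a by-arm count of patients with a diuretic started, or its dose increased, after Day 1.

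The cost is one term list and two tables from data already collected. No dose, diuretic or stopping rule changes. The downside is that the combined rate includes background disease events in both arms. The placebo column shows how many, and keeping the nonspecific terms separate limits the blurring.
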